3. OVERALL STUDY DESIGN AND PLAN

This is a Phase 3, double-blind, randomized, placebo-controlled, multicenter, international, parallel group study to evaluate the safety, tolerability, and efficacy of mavacamten compared with placebo (1:1) in participants with symptomatic oHCM. Approximately 220 participants will be enrolled. This includes ~80 participants (~40 per treatment group) who consent to participate in a CMR substudy at selected sites. Randomization will be stratified according to New York Heart Association (NYHA) functional classification (II or III) (i.e. NYHA class II or III), current treatment with β -blocker (yes or no), planned type of ergometer used during the study (treadmill or exercise bicycle), and consent for the CMR substudy (yes or no).

The expected study duration is approximately 43 weeks: up to 5 weeks for screening, a 30-week treatment period, and an 8-week post-treatment follow-up period (± 7 days).

4. RANDOMIZATION AND BLINDING PROCEDURES

4.1. Randomization

Participants who meet the inclusion/exclusion criteria will be randomized via an interactive response system (IXRS) in a 1:1 ratio to receive double-blind treatment with either mavacamten 5 mg or matching placebo QD. Randomization will be stratified according to NYHA class (II or III), current treatment with β -blocker (yes or no), type of ergometer (treadmill or exercise bicycle), and consent for the CMR substudy (yes or no).

4.2. Study Blinding

Participants will be randomized to receive mavacamten or matching placebo in a double-blind manner such that the principal investigator; site staff, including the pharmacist; and the participant will not know which study drug is being administered. In addition, the sponsor, the central and core laboratories, and clinical site monitors will be blinded to assigned treatment. Mavacamten and matching placebo will be identical in appearance to preserve the blind. Study drug (mavacamten or matching placebo) will be labeled with a unique identifying number that will be assigned to a participant through the IXRS.

Blinded results (ie, echocardiography results, and PK data) will be transferred to the IXRS by the respective core laboratories in order to perform dose adjustments and dose discontinuations in a blinded manner. In addition, sham dose discontinuation and unscheduled visits, if necessary, will be performed in the placebo arm to preserve the blind. However, site personnel who perform specific tasks, such as reviewing echocardiograms for safety, may be unblinded (see Study Reference Manual). In the case of LVEF $\leq 30\%$ the investigator will be notified as described in Section 7.3.3 of the protocol. The pharmacovigilance team will be unblinded for suspected unexpected serious adverse reaction (SUSAR) reporting. The IDMC may also be unblinded to treatment allocation and all safety and efficacy data.

4.3. Methods for Unblinding

All efforts should be made to keep participants blinded to treatment assignment. However, participants may be unblinded to treatment assignment upon request from the Investigator and agreement by the sponsor if knowledge of treatment assignment will impact future treatments or clinical care of the participant. Unblinding by the investigator independently of the sponsor also may occur if an adverse event (AE) or toxicity necessitates identification of the study drug for the welfare of the participant. Please refer to the Suvoda Interactive Web Response System Manual for the unblinding process and contact information.

5. DETERMINATION OF SAMPLE SIZE

Approximately 220 participants will be randomized, with 110 participants in each of the 2 groups. Randomization will be stratified for NYHA class (II or III), current treatment with β -blocker (yes/no), type of ergometer (treadmill or exercise bicycle), and consent for the CMR substudy (yes or no). The sample size should provide adequate power to determine the superiority of mavacamten in improving peak oxygen consumption (pVO₂) and NYHA class relative to placebo (see Section 12.2.1 of the protocol). The power calculation is derived

assuming a true clinically meaningful difference of 25% between mavacamten and placebo participants in achieving the clinical response. Based on the MYK-461-004 PIONEER-HCM Phase 2 study, 50% of the participants receiving mavacamten met the clinical responder definition by the end of 12-week treatment period. Assuming the same percentage of participants in the active treatment arm and 25% in placebo arm will achieve the clinical response at the end of the 30-week dosing period in the current study, the proposed sample size of 110 participants per arm will provide 96% power at the 2-sided 5% statistical significance level. Participants who terminate early or cannot be assessed for the clinical response at the end of the 30-week dosing period will be considered nonresponders.

6. GENERAL STATISTICAL CONSIDERATIONS

The primary analysis will be conducted through the 30-week treatment period. Data collected through this time point will be cleaned and locked prior to conducting the primary analysis.

Once all participants have completed their Week 38/end of study (EOS) visit, all data will be cleaned and locked, and analyses using this data will be used to inform study objectives relating to follow-up safety and reversibility of drug effect.

SAS® version 9.4 or higher will be used for statistical analyses, tabulations, and graphical presentations.

In general, descriptive summaries will be presented by treatment group (placebo and mavacamten) for values at each visit. The descriptive summary for continuous variables will also be provided for the change from baseline and, if appropriate, for the change from week 30 to week 38. Summaries of continuous variables will include the number of subjects (N), mean, standard deviation (SD), median, Q1, Q3, minimum, and maximum. For variables with highly skewed distribution (e.g. log-normal distribution), geometric mean and %CV will also be reported in descriptive summaries. Inferential analysis for those variables may be performed after log-transformation as deemed appropriate. Descriptive summaries for categorical variables will include the number and percentage of subjects. Unless otherwise stated, denominators for percentages will be the number of subjects in the analysis population.

Between-group comparisons will focus on the comparative performance of mavacamten versus placebo. All statistical tests will be conducted at a 2-sided significance level of 0.05.

In general, baseline is defined as the last nonmissing value on or before the first dose date and time (as applicable). For certain data types (eg, accelerometer, PROs, cardiac rhythm monitoring, etc.), special considerations may be required. Refer to the specific data section for details.

Unless otherwise noted, nonsafety (ie. efficacy, pharmacodynamics [PD]) information displayed “by visit” will utilize analysis visits as defined by the analysis visit window as opposed to the visits at which the information was collected (ie, nominal visit). Data collected at unscheduled or early termination (ET) visits will also be mapped to analysis visits. The analysis day for the purposes of deriving the analysis visit windows are derived as follows (reference date is the study drug initiation date, or the randomization date if the study drug initiation date is missing):

- If date of information (year, month, and day) is completely missing, analysis day cannot be calculated and will be treated as missing. If the date is partially missing, date will be imputed according to the rules outlined in [Section 6.4](#).
- If date is < reference date, analysis day = date of information – reference date. If date \geq reference date, analysis day = (date of information – reference date) + 1.

The visit windows for efficacy and PD assessments will be defined according to their respective collection schedules. The rule for defining the analysis window is +/-14 days from the target visit date for all post-baseline visits, except for Week 30 and Week 38, which have +/- 28 day windows. If 2 adjacent visit windows overlap, the limits of the windows will be adjusted to the midpoint between the 2 visits. The specific window definitions for each endpoint are available in Appendix 2 [Table 3 to Table 9](#).

For efficacy and PD analyses, if a value does not fall within an analysis window, it will not be included in the summary analysis. However, these values will be included in data listings and SAS data sets. For post-baseline data, when more than 1 value is available within the same analysis visit, the value collected closest to the target visit day will be used for analysis. If 2 values are the same distance to the closest to target visit day (for example, 1 value is before and the other value is after the target day), then the latest value will be selected as the analysis value. For a specific analysis window, if the latest collected time point has 2 or more values collected, then for continuous data, the average among these results will be derived, and for categorical data (eg, yes or no) the clinically ‘worse’ value will be selected.

Safety data and PK data will be summarized by the nominal visit (per protocol), and unscheduled visits will be presented in listings only. If a participant had treatment early terminated (ET) and had additional visits after the ET visit, those visits will be relabeled as FU (ie, follow-up)-1, FU-2, and FU-3, etc. at 4-week intervals following the ET visit.

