- c The ET visit will be scheduled as soon as possible after the participant permanently discontinues study drug. The participant will be encouraged to participate in the remaining scheduled study visits, particularly the Week 30 visit and the Week 38/EOS visit. If a participant permanently discontinues treatment at or before Week 22, the final visit will be at Week 30.
- d At Screening, ET, Week 30/EOT, and Week 38, a complete physical examination will be conducted, including a neurological examination. At all other visits, an abbreviated cardiopulmonary physical examination will be conducted, with other systems assessed as directed by interval history.
- e Changes in baseline conditions from once the ICF is signed will be recorded as an AE. All changes unless otherwise specified that occur after the administration of study drug will be considered treatment-emergent AEs. This assessment will occur either by phone call or an in-person visit.
- f For participants who have ICDs, information including rhythm strips and events will be downloaded from the ICDs at baseline, at Week 12, and at Week 30, or as clinically indicated after any ICD discharge interrogation occurring during the double-blind treatment period.
- g Twelve (12)-lead ECGs will be performed after 10 minutes of rest at Screening and prior to dosing at all onsite study visits (except Weeks 8 and 14). Each time an ECG is completed, a 10-second paper ECG will be obtained and maintained in the study participant's source documentation. QTcF value from Day 1 ECG will not be used for eligibility or for temporary discontinuation. The Day 1 QTcF value will be used as the baseline to determine percent change at future visits when criteria for temporary discontinuation are applied. (Note: If for any reason a D1 QTcF is not determined, then QTcF from screening ECG will be used in percent change calculation.)
- h At Screening, ET, Week 30/EOT, and Week 38, complete vital signs including temperature, HR, respiratory rate, and BP will be obtained. At all other visits, only HR and BP are required. If PK sampling is conducted at a visit, vital signs should be collected before PK sampling. Vital signs should be taken with the study participant in the same position at all visits. BP should be taken via an automated recorder after resting for at least 5 minutes.

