6.2. Analysis Populations

Four analysis populations are defined in this study:

- Intention-to-treat (ITT) Population: All randomized subjects, regardless of whether they receive study drug, with analyses conducted according to randomized treatment assignment

- Safety Analysis Population: All randomized subjects who receive at least 1 dose of study drug with analyses conducted by actual treatment received.
- PK Analysis Population: All randomized subjects who receive at least 1 dose of mavacamten

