6.4. Missing Data

In general, missing data will not be imputed unless specifically stated in this SAP. For mixed-model repeated-measure analyses, missing data are handled implicitly by the model. For the responder analysis of primary and secondary endpoints, refer [Section 8.1](#) and [8.2](#) for the specific handling rules.

Handling of Missing Data:

- For values below the lower limit of quantitation (LLOQ), 1/2 LLOQ will be imputed unless otherwise specified.
- For values above the upper limit of quantitation (ULOQ), ULOQ + 1 unit of significant digit will be imputed unless otherwise specified.
- In general, for missing or partial dates the following is noted:
 - Start Dates:
 - If day is missing, then impute it to be the start of the month (eg, 01 MMM YYYY); except if the month and year is equal to the first dose date month and year then impute the day to be the same day as the first dose date.
 - If month is missing, then impute it to be the start of the year (eg, 01 JAN YYYY), except if the year is equal to the first dose date year then impute the day and month to be the same as the first dose date.
 - If year is missing, then do not impute.
 - End Dates:
 - If day is missing, then impute it to be the end of the month (eg, 31 MMM YYYY), except if the month and year is equal to the last

assessment date month and year then the day should be imputed to the last assessment date day.

- If month is missing, then impute it to be the end of the year (eg, 31DECYYYY), except if the year is equal to the last assessment date year then the day and month should be imputed to the last assessment date day and month.
- If year is missing then do not impute.
- For all other type of dates:
 - If only day is missing, then impute it to be the start of the month (eg, 01MMMYYYY).
 - If month and day are missing, then impute it to be the start of the year (eg, 01JANYYYY).
 - If year is missing, then do not impute.

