10.2.3. Categorical Analysis

The number and percentage of subjects with maximum post-dose QTcF values > 450 msec, > 480 msec, > 500 msec, > 520 msec, and > 550 msec will be summarized by treatment group. Participants with QTcF values > 500 msec will be listed along with corresponding baseline values, Δ QTcF, and baseline and treatment HR. The number and percentage of subjects with QTcF increase from baseline > 30 msec and > 60 msec will be summarized by treatment group.

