10.5. Cardiac Rhythm Monitoring (Including Holter Monitor)

The summary statistics of maximum HR, atrial fibrillation (Afib) percentage time, and VT (sustained or non-sustained) frequency will be calculated for each cumulative 48-hour Holter monitoring period and summarized by treatment group and visit. For each of the cardiac event type (Afib and VT), the number of subjects with ≥ 1 occurrence will be summarized. The percentage of time in Afib and number of VT episodes per subject will also be summarized. Additional parameters (eg, supraventricular tachycardia, premature ventricular contractions, pauses) may be summarized and analyzed as appropriate.

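### The SAP's default percentage denominator is the whole analysis population, with no readable override for measured safety categories, so by-visit safety percentages will be understated wherever assessments are missing

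*SAP*

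**What the plan says.** SAP Section 6 states the default: "Unless otherwise stated, denominators for percentages will be the number of subjects in the analysis population". The same section asks for counts and percentages for categorical variables and sets the layout: "In general, descriptive summaries will be presented by treatment group (placebo and mavacamten) for values at each visit".

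For safety tables the population is the Safety Analysis Population of SAP Section 6.2: "All randomized subjects who receive at least 1 dose of study drug with analyses conducted by actual treatment received". No post-baseline measurement is required. On missing values, Section 6.4 says: "In general, missing data will not be imputed unless specifically stated in this SAP". It has no rule for a participant with no measurement in a safety table.

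On visits, SAP Section 6 says: "Safety data and PK data will be summarized by the nominal visit (per protocol), and unscheduled visits will be presented in listings only". Visits attended after an early termination (ET) visit are relabelled FU-1, FU-2 and so on, at four-week steps. Protocol Table 1, footnote c, adds: "If a participant permanently discontinues treatment at or before Week 22, the final visit will be at Week 30".

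The measured safety categories in the readable part of SAP Section 10 are these. None states its own denominator.

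- **Section 10.5, rhythm monitoring.** The statistics "will be calculated for each cumulative 48-hour Holter monitoring period and summarized by treatment group and visit". A count of participants with at least one episode of each event type follows.
- **Section 10.3, laboratory.** Shift tables from baseline.
- **Section 10.2.3, QTcF.** "The number and percentage of subjects with maximum post-dose QTcF values" above five thresholds, plus increases of more than 30 and more than 60 msec.
- **Section 10.3.1, liver tests.** Elevation categories over the treatment-emergent period.

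Two uses of the full population are deliberate. Protocol Section 12.4.8.1 names the safety population as the denominator for adverse events, and SAP Section 5 counts unassessable participants as nonresponders on the primary endpoint.

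**The concern.** A full-population denominator suits adverse events, which can be reported at any time, and a responder endpoint with a stated nonresponder rule. It does not suit a finding that can be seen only if a test is done. A participant with no Week 26 Holter recording adds one to the denominator and cannot add to the numerator. The arithmetic is the same as if the recording had been made and was clean.

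Some of this missingness is built into the design. Participants who stop drug at or before Week 22 have no Week 38 visit, so they cannot contribute to a Week 38 category, yet the default keeps them in its denominator. Early stoppers who do attend later visits have those visits moved to FU labels. They leave the numerators of the nominal visits and stay in the denominators. Any FU-visit percentage would be divided by the whole arm, although only early stoppers can have such a visit.

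SAP Section 10 plans no safety hypothesis tests, so readers will compare the arms largely on these percentages. Atrial fibrillation or flutter and ventricular tachyarrhythmias are named safety endpoints (Protocol Section 12.2.5), and the Holter device is applied on treatment only at Weeks 12 and 26 (Protocol Table 1, footnote l).

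**Working it through.** The plan states no safety event rate and no expected missingness, so there is no figure to reproduce.

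**Inputs**

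- N = 110 per arm (SAP Section 5), taking all randomized participants as dosed.
- Denominator N by default (SAP Section 6).
- n = participants assessed, x = participants with the finding, m = 1 - n/N.
- The values of m and the underlying rates are assumptions.

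**Formula**

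Reported percentage = x/N = (x/n) × (n/N) = (rate among assessed) × (1 - m).

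The shortfall in points is rate × m. It is zero when m = 0.

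**Size within one arm**

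| Rate among assessed | m = 0 | m = 2% | m = 5% | m = 10% | m = 20% |
|---|---|---|---|---|---|
| 5% | 5.0% | 4.9% | 4.75% | 4.5% | 4.0% |
| 10% | 10.0% | 9.8% | 9.5% | 9.0% | 8.0% |
| 20% | 20.0% | 19.6% | 19.0% | 18.0% | 16.0% |

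In counts, 11 findings in an arm of 110 print as 11/110 = 10.0%. If 11 participants were unassessed, the rate among those assessed is 11/99 = 11.1%.

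**Which m applies to which table**

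- *QTcF and liver categories.* These use any post-dose value, so m is the share of dosed participants with no post-dose value at all. Protocol Table 1 schedules post-dose ECGs at eight visits (Weeks 4, 6, 12, 18, 22, 26, 30 and 38) plus ET, and chemistry at four (Weeks 6, 18, 30 and 38) plus ET. If m is 0-5%, a 10% finding loses 0 to 10% × 5% = 0.5 points.
- *By-visit categories.* Here m includes everyone not assessed at that visit. If m is 10-20%, a 10% finding loses 10% × 10% = 1 point to 10% × 20% = 2 points.
- *FU visits.* Here m can be close to 1. As an invented example, 2 findings among 8 participants at FU-1 is 2/8 = 25%, but the default gives 2/110 = 1.8%.

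**Comparison between arms**

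If the rate among those assessed is the same in both arms, the reported risk ratio is (1 - m for mavacamten)/(1 - m for placebo).

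| m, mavacamten | m, placebo | Reported ratio when the true ratio is 1 |
|---|---|---|
| 2% | 2% | 0.98/0.98 = 1.00 |
| 5% | 2% | 0.95/0.98 = 0.97 |
| 10% | 3% | 0.90/0.97 = 0.93 |
| 15% | 5% | 0.85/0.95 = 0.89 |
| 5% | 10% | 0.95/0.90 = 1.06 |

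**The case against.** The strongest reply is that the SAP specifies few by-visit safety percentages. ECG intervals, vital signs and by-visit laboratory values are continuous summaries with no percentage. QTcF and liver categories take any post-dose value, so one missed visit removes nobody who has another result. Holter monitoring is not done at Week 38, so the only visible candidate there is a laboratory shift table. The SAP does not say whether shift tables carry percentages or a missing row, and Section 10.5 asks for a number of participants. This stands and sets the scope. It does not remove the point, because Section 6 asks for percentages with categorical counts and the readable text offers no other denominator.

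A second reply is that findings divided by all treated participants is a legitimate incidence, and that an assessed-only rate assumes the missingness is uninformative, which is doubtful after discontinuation. That is fair, and it is why the number not assessed should be shown whichever denominator is used.

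A reader might also infer more than the documents support:

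- *That every percentage is affected.* The rule is a default with an exception clause, and it is the intended choice for adverse events and the primary response.
- *That the SAP classes unassessed participants as free of the finding.* It does not, and missing values are generally not imputed. The effect comes only from the arithmetic.
- *That NYHA class percentages are wrong.* SAP Section 6.4 sends responder handling to Sections 8.1 and 8.2, which are redacted, so their denominators cannot be judged.
- *That dose holds create unassessed participants.* Protocol Section 7.3.2 brings them back for repeat ECG, PK and echocardiography.
- *That the rule makes mavacamten look safer.* Nothing in the documents says which arm will have more missing assessments.

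**Conclusion.** The point holds in a limited form. SAP Section 6 makes the whole analysis population the default denominator, and the readable Section 10 does not override it for measured safety categories. Wherever assessments are missing, such a percentage is understated by the factor (1 - m).

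The exposure is mainly in four places: Holter occurrence at Weeks 12 and 26, any by-visit laboratory shift percentages, any Week 38 category, and visits relabelled FU after early termination. At Week 38 part of the shortfall is fixed by design. For the QTcF and liver tables it is probably small.

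The sizes rest on assumed missingness: 0-0.5 points on a 10% finding at m of 0-5%, and 1-2 points at 10-20%. In the assumed unequal cases the reported risk ratio ran from 0.89 to 1.06 with no true difference, so the direction of any shift between arms is unknown. Redacted SAP sections may contain exceptions that cannot be seen. The sample size and the primary analysis are not affected.

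**What to change.** Replace the denominator sentence in SAP Section 6 with text to this effect:

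> For adverse event incidence and responder endpoints, percentages are based on the analysis population. For measured safety categories taken over the post-baseline period (QTcF, liver tests), they are based on participants with one or more evaluable post-baseline values. Change and shift categories also require a baseline value. For categories shown by visit, including Week 38 and FU visits, they are based on participants assessed at that visit. Each table shows the numbers assessed and not assessed, by arm.

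Sections 10.2.3, 10.3, 10.3.1 and 10.5 should each point to this rule and say whether percentages are shown.

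The cost is SAP wording and table-shell work, with no new data. The drawback is that assessed-only rates take missingness to be uninformative. The not-assessed counts let the reader judge that, and recover the full-population percentage if preferred.
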